7 NIH REPORTING REQUIREMENTS/DATA AND SAFETY MONITORING PLAN

7.1 DEFINITIONS

Please refer to definitions provided in Policy 801: Reporting Research Events found at: <https://irbo.nih.gov/confluence/pages/viewpage.action?pageId=36241835#HRPPolicies-800Series-ComplianceandResearchEventReportingRequirements>.

7.2 OHSRP OFFICE OF COMPLIANCE AND TRAINING / IRB REPORTING

7.2.1 Expedited Reporting

Please refer to the reporting requirements in Policy 801: Reporting Research Events and Policy 802: Non-Compliance Human Subjects Research found at: <https://irbo.nih.gov/confluence/pages/viewpage.action?pageId=36241835#HRPPolicies-800Series-ComplianceandResearchEventReportingRequirements>.

7.2.2 IRB Requirements for PI Reporting at Continuing Review

Please refer to the reporting requirements in Policy 801: Reporting Research Events found at: <https://irbo.nih.gov/confluence/pages/viewpage.action?pageId=36241835#HRPPolicies-800Series-ComplianceandResearchEventReportingRequirements>.

7.3 NCI CLINICAL DIRECTOR REPORTING

Problems expeditiously reviewed by the OHSRP in the NIH eIRB system will also be reported to the NCI Clinical Director/designee; therefore, a separate submission for these reports is not necessary.

In addition to those reports, all deaths that occur within 30 days after receiving a research intervention should be reported via email unless they are due to progressive disease.

To report these deaths, please send an email describing the circumstances of the death to [REDACTED] within one business day of learning of the death.

7.4 NIH REQUIRED DATA AND SAFETY MONITORING PLAN

7.4.1 Principal Investigator/Research Team

The clinical research team will meet weekly when patients are being actively enrolled on the trial to discuss each patient.

All data will be collected in a timely manner and reviewed by the principal investigator or a lead associate investigator. Events meeting requirements for expedited reporting as described in Section [7.2.1](#) will be submitted within the appropriate timelines.

The principal investigator will review adverse event and response data on each patient to ensure safety and data accuracy. The principal investigator will personally conduct or supervise the investigation and provide appropriate delegation of responsibilities to other members of the research staff.

8 STATISTICAL CONSIDERATIONS

8.1 STATISTICAL HYPOTHESIS

Primary Endpoint:

- Determine if Bethesda protocol provides improved sensitivity for detection of early-stage gastric cancer in *CDH1* germline mutation carriers compared to the Cambridge method.
- Secondary Endpoints:
- Define the false negative rate of SRCC detection using Bethesda and Cambridge methods in patients who proceed to risk-reducing total gastrectomy.
- Estimate and compare the difference in crude cancer detection rates between endoscopy using the Bethesda protocol and the Cambridge method.

Based on the prior experience with surveillance endoscopy, out of 110 patients, only 17+24=41 (37%) patients underwent a gastrectomy. To provide adequate patients to have a high probability of yielding 60 per arm who have a gastrectomy resulting in 48 with SRCCs, the study will randomize 175 patients to Bethesda protocol and 175 to Cambridge (350 total patients) in order to have 79% probability of obtaining 60 or more patients undergoing each procedure including gastrectomy, if the true probability of undergoing a gastrectomy is 37%. In practice, patients will continue to be randomized up to the limit of 350 total randomized patients, or until 48 patients on each arm have undergone a total gastrectomy and found to have SRCCs. Re-enrolled subjects will be counted separately at each enrollment/randomization.

All randomized patients who receive an endoscopy will have the crude cancer detection rates compared between the two methods. Data from a prior NIH trial indicated that the crude cancer detection rate was 15% using the Cambridge method and 36% using the Bethesda method, based on 26 and 109 evaluable patients respectively. In the present trial, if all 175 patients are required in each arm, then there would be 90.6% power to detect a difference with a two-sided 0.05 significance level between 15% and 30% crude cancer detection rates on the Cambridge method and the Bethesda protocol respectively. If only 135 evaluable patients undergo endoscopy using each method, there would be 81.0% power to detect a difference with a two-sided 0.05 significance level between 15% and 30% crude cancer detection rates.

Since January 2017 through September 2019, we have enrolled over 240 *CDH1* mutation patients on protocol 17-C-0043, performed over 145 surveillance endoscopies (12 performed in September 2019), over 61 risk-reducing gastrostomies (5 performed in September 2019). It is anticipated that more than 100 patients per year will be able to enroll onto this trial. Thus, accrual of up to 350 total subjects is expected to be completed in no more than 3.5 years.

8.3 POPULATIONS FOR ANALYSES

All patients who are randomized on the trial and receive an endoscopy will be used for analysis. Those who undergo gastrectomy will be included in the evaluation of the two methods relative to the biopsy proven results.

8.4 STATISTICAL ANALYSES

8.4.1 General Approach

The patients who undergo gastrectomy will have the sensitivity, and false negative rates of detection of SRCC determined, while all patients undergoing an endoscopy will be used to estimate and compare the crude cancer detection rates for the two methods.

8.4.2 Analysis of the Primary Endpoint

The primary objective of the study is to determine if Bethesda protocol provides improved sensitivity for detection of early stage gastric cancer in *CDH1* germline mutation carriers compared to the Cambridge method. Among patients who undergo gastrectomy, in each of the two arms, the fraction of patients who had SRCCs previously identified by endoscopic biopsy out of those who had SRCCs detected on final pathologic analysis of gastrectomy explants will be used to determine the sensitivity of each arm. These fractions will be reported along with a 95% confidence interval and will be compared between the two arms using a two-tailed Fisher's exact test. This analysis

will also be carried out after 24 evaluable participants on each arm have undergone a total gastrectomy and found to have SRCCs as an interim evaluation, as indicated below in Section **8.4.5**.

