1.2 BACKGROUND AND RATIONALE

1.2.1 Study Disease

Heredity diffuse gastric cancer (HDGC) accounts for approximately 1-3% of gastric cancers globally and is the most common familial form of gastric cancer [1]. Forty percent of HDGC cases are linked to inactivating germline mutations in the E-cadherin (*CDH1*) tumor suppressor gene [2]. Estimates of disease penetrance have demonstrated *CDH1* mutation carriers have a substantially elevated lifetime risk of developing gastric cancer, approximating 37-70% in men and 24-56% in women [3, 4].

The *CDH1* gene encodes the tumor-suppressor protein E-cadherin, which is a glycoprotein localized on the surface of epithelial cells at the adherens junctions [5]. E-cadherin functions to regulate cell-cell adhesion and intercellular communication, which is critical for cellular migration, proliferation, apoptosis and cell differentiation [6-10]. When E-cadherin function is compromised there is loss of cell polarity and epithelial architecture, which interferes with the integrity of the adherens junctions. *CDH1*-null epithelial cells may become inappropriately placed in the cellular matrix of the lamina propria resulting in the formation of signet ring cancer cells (SRCC) (**Figure 1** and **Figure 2**) [11]. It is postulated that gastric *CDH1*-null SRCC can exist for extended periods of time allowing for the accumulation of additional molecular alterations that lead to tumorigenesis and/or metastasis [12]. It is speculated that a second hit to this gastric mucosa, via mutations in *Smad4*, *RHOA*, or *TP53*, ultimately enables tumor cell invasion and metastatic potential [11, 13-15].

Because of the increased lifetime risk of developing gastric cancer, the International Gastric Cancer Linkage Consortium (IGCLC) recommends risk-reducing total gastrectomy to remove all gastric epithelium [3]. At the time of total gastrectomy almost all asymptomatic patients with *CDH1* mutations are found to have SRCC within the stomach. Since 2017, our team has evaluated more than 59 total gastrectomy explants and found 86% harbor SRCC (T1a gastric cancers) on final pathology. However, there is a scientific lack of understanding of how and why these SRCC become invasive cancer.

[figure not shown]

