The analysis consisted of 110 patients with the *CDH1* mutation who were evaluated at NIH Clinical Center. All 110 patients underwent screening gastroscopy; 29 using the Cambridge method and 81 using the Bethesda protocol. Signet ring cancer cells were detected in 4 patients (13.8%) using Cambridge method and 29 (35.8%) with the Bethesda protocol. Over half (17/29) of the Cambridge method patients underwent prophylactic total gastrectomy, of whom 11 had SRCC identified on final pathology. Of those 11, only 2 were positive for SRCC on esophagogastroduodenoscopy (EGD) yielding an 82% (9/11) false negative biopsy rate and an overall sensitivity of 18% (2/11). Comparatively, 24 patients screened with the Bethesda protocol (24/81) later underwent prophylactic total gastrectomy, of whom 22 were found to have SRCC on final pathology. Of those 22, 13 were positive for SRCC on EGD giving the Bethesda protocol a 41% (9/22) false negative biopsy rate and an overall sensitivity of 59% (13/22) for detecting SRCC. Based on these data, we conclude the Bethesda protocol is likely better than the Cambridge method at detecting SRCC in asymptomatic *CDH1* mutation carriers.

Our primary objective with this prospective random-assignment study is to compare the Bethesda protocol (investigational) to the Cambridge method (control) for detection of early stage gastric cancer (e.g. SRCC) in asymptomatic CDH1 mutation carriers.

To fully understand the limitations of endoscopic gastric cancer surveillance, the false-negative cancer detection rate should be defined also, which is a secondary aim of the proposed study. This can only be done through complete pathologic examination of total gastrectomy explants from patients who choose to proceed to prophylactic surgery endoscopic surveillance.

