3.3 FOLLOW-UP

Patients will return to the NIH Clinical Center approximately two weeks after the EGD to discuss pathology results and any adverse events that they might have experienced. Alternatively, we will discuss pathology results and adverse events (AEs) on the phone.

Gastrectomy is not part of this protocol, but if patient elects to undergo gastrectomy on another protocol, we may perform additional correlative studies before, during and after gastrectomy, including pathology assessment of stomach tissue.

Participants declining total gastrectomy (TG) may be invited to collect stool samples after study intervention as indicated in Section [5.1](#).

Participants who elect for TG may be invited to collect stool, blood and oropharyngeal swab/saliva samples pre-gastrectomy and post-gastrectomy as indicated in Section [5.1](#).

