5.1.1.3 Stool/Microbiome by DNA + RNA Sequence Analysis

Stool specimens will be collected in all study participants.

In those who decline total gastrectomy: the participant will be asked to produce a single stool specimen, to be collected one time prior to or on the day of study intervention (i.e., EGD), followed by potential stool specimen collection twice more post-study intervention (EGD), as applicable per PI discretion (refer to the Section [5.1](#) specimen collection table).

In those who elect surgery: the participant will be asked to produce a single stool specimen, to be collected one-time pre-gastrectomy prior to the endoscopy, then two times post-gastrectomy (refer to the Section [5.1](#) specimen collection table).

Stool specimens will be collected in a standardized manner using a stool collection kit ([Appendix 3](#)). Received participant collection kit stool samples will be aliquoted by the research study team into 3 cryotubes containing approximately 300 mg of stool per tube (i.e., n=3 total, if possible

based provided specimen volume only). These samples must be stored at -80°C *within 24 hours after collection* and kept frozen until further analysis. Samples will be initially stored in the Blood Processing Core (BPC).

Note: In circumstances in which a participant is unable to produce a stool sample (i.e., unable to give stool “on demand”) at the indicated timepoint, one or more additional scheduled stool sample collection request(s) are permitted to meet study requirements for the collection of the sample per PI discretion.

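### The primary sensitivities come only from patients who elect off-protocol gastrectomy, and the plan has no check on whether the biopsy result drives that choice

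*Combined protocol and SAP*

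**What the plan says.** - **Primary analysis.** Section 8.4.2 takes, among patients who undergo gastrectomy, "the fraction of patients who had SRCCs previously identified by endoscopic biopsy out of those who had SRCCs detected on final pathologic analysis" of the explant. It reports each fraction with a 95% confidence interval and compares arms by a two-tailed Fisher's exact test. Section 8.3 restricts the population in the same way: "Those who undergo gastrectomy will be included in the evaluation of the two methods relative to the biopsy proven results". The false-negative rates in Section 8.4.3 come from the same subset.
- **Who is verified.** Section 3.3 says "Gastrectomy is not part of this protocol, but if patient elects to undergo gastrectomy on another protocol", further correlative work may be done. It also says "Patients will return to the NIH Clinical Center approximately two weeks after the EGD to discuss pathology results", with a telephone call as the alternative.
- **Reasons for surgery unrelated to the biopsy.** Section 1.2.1 says the international consortium "recommends risk-reducing total gastrectomy to remove all gastric epithelium" for carriers as such. Section 5.1.1.3 asks patients electing surgery for a stool sample "to be collected one-time pre-gastrectomy prior to the endoscopy, then two times post-gastrectomy", although the table in Section 5.1 also allows that sample within three months before surgery.
- **An analysis in all endoscoped patients.** Sections 8.2, 8.4.1 and 8.4.3 plan a Fisher comparison of crude detection rates in all randomised patients who have an endoscopy.
- **What Sections 8.3 to 8.4.6 do not contain.** There is no table of gastrectomy uptake by arm and biopsy result, no correction for selective verification and no robustness analysis. Baseline data are to be reported overall and by arm (Section 8.4.4), not by gastrectomy status.

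**The concern.** Randomisation protects a comparison of everyone endoscoped. It does not protect a subset that forms after the test result is known. If a positive biopsy makes surgery more likely, true positives are over-represented among the explants, and the raw fraction overstates sensitivity. If the push towards surgery is the same in both arms, both estimates shift but the test of equality remains valid. If it differs by arm, a difference in the choice of surgery can look like a difference between the endoscopy methods, or can hide one. The primary endpoint and the false-negative rates both depend on this, and the plan does not say how a reader would find out which case applies.

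**Working it through.** **1. The plan's own figures reproduce.** Exact power of the two-sided Fisher test at 48 per arm, 30% v 60%, level 0.05, is 80.05% (Section 8.2 states 80%). For crude detection at 15% v 30%, it is 90.65% at 175 per arm and 80.99% at 135 per arm (stated 90.6% and 81.0%). The gap is not an arithmetic error.

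**2. Effect of selective uptake.** Let s be the true sensitivity and r the gastrectomy rate after a positive biopsy divided by that after a negative one. If uptake depends only on the biopsy result, the raw fraction estimates s·r / (s·r + 1 − s).

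- Same r = 2 in both arms: 0.6/(0.6 + 0.7) = 46% and 1.2/(1.2 + 0.4) = 75%, in place of 30% and 60%. The level stays near 3% and power is 77%.
- Different r, with true sensitivity 40% in both arms and Cambridge r = 1 (exact Fisher, 48 per arm):

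| Bethesda r | Bethesda raw fraction | Probability of rejection |
|---|---|---|
| 1 | 40% | 2.9% |
| 1.25 | 45% | 5.5% |
| 1.5 | 50% | 12% |
| 2 | 57% | 32% |

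- Reverse case, true 30% v 60%, Cambridge r = 2, Bethesda r = 1: the test sees 46% v 60%, and power falls from 80% to 21%.

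**3. What the background series shows about r.** Inputs are from Sections 1.2.2 and 8.2. For Bethesda, "24 patients screened with the Bethesda protocol (24/81) later underwent prophylactic total gastrectomy, of whom 22 were found to have SRCC on final pathology", and "Of those 22, 13 were positive for SRCC on EGD". I use the counts as Section 1.2.2 defines them, which matches Section 8.4.2.

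| | Endoscoped | Biopsy + | Gastrectomy: biopsy + / − | SRCC on explant: biopsy + / − |
|---|---|---|---|---|
| Cambridge | 29 | 4 | 2 / 15 | 2 / 9 |
| Bethesda | 81 | 29 | 13 / 11 | 13 / 9 |

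- Cambridge r = (2/4)/(15/25) = 0.83. Bethesda r = (13/29)/(11/52) = 2.12. Ratio of ratios: 2.54.
- Variance of its logarithm = (1/2 − 1/4) + (1/15 − 1/25) + (1/13 − 1/29) + (1/11 − 1/52) = 0.391, giving a 95% CI of 0.75 to 8.7, p = 0.14.
- At these ratios, with true sensitivity 40% in both arms, rejection would be 54%. That is fragile: had the 17 Cambridge gastrectomies split 3 + 14 it would be 15%, and at 4 + 13 it would be 3.5%.

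**4. A corrected estimate on the same data.** Begg-Greenes applies the explant-positive fraction in each biopsy group to everyone in that group.

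- Cambridge: 4/(4 + 25 × 9/15) = 4/19 = 21.1% (raw 2/11 = 18%).
- Bethesda: 29/(29 + 52 × 9/11) = 29/71.5 = 40.5% (raw 13/22 = 59%).
- The gap falls from 41 to 19 points (bootstrap 95% interval about −6 to +42).
- Tipping point: among biopsy-negatives, let k be the gastrectomy rate in patients with SRCC divided by that in patients without. Replace d/(d + e) by (d/k)/(d/k + e), where d and e are explants with and without SRCC. For k from 0.5 to 2.5, Cambridge runs from 17.6% to 29.9% and Bethesda from 38.3% to 46.5%. The gap is 16.5 to 20.7 points with a common k, and 8.4 to 28.9 if k may differ by arm.

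**5. How far crude detection helps.** With SRCC prevalence balanced by randomisation and negligible biopsy false positives, the crude rate is prevalence × s, so the ratio of crude rates estimates the ratio of sensitivities without verification. In the series, all 15 biopsy-positives who had surgery had SRCC on the explant (exact 95% lower bound 78%). I simulated the Section 8.2 stopping rule with 4,000 runs per case, assuming 80% prevalence and 37% gastrectomy. With equal true sensitivities, crude detection rejected in 4.7% to 4.8% of runs. It was non-significant in 90% to 96% of the false primary rejections at r = 1.5, r = 2 and the background ratios. The simulation left out the interim look and re-enrolment.

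**The case against.** The strongest reply is that the crude comparison is already planned and powered, and Section 8.4.1 places it beside the sensitivity analysis. A reader might infer from the gap that nobody could tell whether the methods or the choice of surgery produced the result. The documents do not support that: by the check above, a between-arm artefact would usually show as a disagreement with crude detection. What remains is that the plan gives the crude comparison no such role, and that it cannot repair the absolute sensitivities or false-negative rates.

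A reader might also infer that the trial has a type I error of 54% (60% in the simulation) because the background ratios would recur. That is unsupported too. The series is retrospective, non-randomised and has four Cambridge biopsy-positives, and its interval for the ratio of ratios includes 1. Nor do the documents show that surgery is always chosen after the result: it is recommended to carriers as such. The stool timing is only weak evidence of earlier decisions.

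Two objections bear on the remedy. Begg-Greenes assumes that, given arm and biopsy result, surgery is unrelated to true SRCC status. As an assumed counter-example, take surgery in 42% of patients with SRCC and 17% of others. The raw fractions are then right, and Begg-Greenes reads 27% v 54% for a true 30% v 60%. The tipping-point formula at k = 0.42/0.17 = 2.47 recovers both values. This objection stands and is why the correction should not replace the primary analysis. Second, a patient may be re-randomised for a second endoscopy (Section 3.3.1) and then have one gastrectomy. A clustered bootstrap handles the variance but does not say which arm that explant verifies. This also stands and needs a rule.

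Finally, the restriction to patients having surgery is disclosed (Sections 1.2.2 and 8.3). Disclosure does not supply the missing check.

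**Conclusion.** The point holds as a gap in the analysis plan that should be fixed. It does not show that the primary test is invalid. If uptake depends on the biopsy result to the same degree in both arms, the test stands and only the reported sensitivities are off, by about 15 points each at r = 2. If the dependence differs by arm, false rejection reaches 12% or 32% in the moderate cases shown, or power falls to 21% in the reverse case. All these error rates are stress cases at 48 per arm, with uptake depending only on the biopsy result. Whether r will differ between randomised arms is unknown, and the 54% to 60% figures at the background ratios should be read only as fragile extremes. Using crude detection as a check rests on balanced prevalence and on negligible or equal biopsy false positives.

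**What to change.** Keep the raw fractions, Fisher test, 48-per-arm target, interim rule and success criterion. Add to Section 8.4.2:

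1. Gastrectomy uptake by arm and biopsy result.
2. As sensitivity analyses, a Begg-Greenes sensitivity per arm and their difference, in all randomised patients with an endoscopy, with a bootstrap clustered by participant because re-enrolled subjects are counted separately (Section 8.2). Add a tipping-point range for k, for example 0.5 to 2.5, also letting k differ by arm. First state one rule for which endoscopy and arm an explant verifies in re-randomised patients. Use gastrectomy status as recorded over the 12-month follow-up in Section 3.5.2.
3. The planned crude detection comparison as the named supportive analysis, reported beside the primary result with its assumptions. Report any disagreement as a limit on the sensitivity conclusion. A crude p below 0.05 is not made a condition for claiming superiority.

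The cost is a little more analysis work, with no new patients or visits. Arm, biopsy result and explant pathology are already needed for the planned endpoints, and the off-study criteria already separate patients who have surgery from those who decline. The sensitivity analyses must wait until the last patients complete the 12-month window, and Begg-Greenes brings its own untestable assumption, which item 2 probes but cannot remove.

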8.4.3 Analysis of the Secondary Endpoint

One secondary endpoint is to define the false negative rate of SRCC detection using Bethesda protocol and Cambridge methods in patients who proceed to risk-reducing total gastrectomy. Among patients who undergo the gastrectomy in each of the two arms, the fraction of patients who had SRCC identified on final pathology but were negative for SRCC on EGD will yield the false negative biopsy rate. These fractions will be reported along with a 95% confidence interval and will be compared between the two arms using a two-tailed Fisher's exact test.

The other secondary endpoint is to estimate and compare the crude cancer detection rates by the two methods. The fractions of SRCCs which are found on endoscopy by the two methods will be reported along with a 95% confidence interval, and the difference in the fractions will be compared using a two-tailed Fisher's exact test.

